# 2. BACKGROUND

## 2.1 Graft Versus Host Disease

In recent years, allogeneic stem cell transplantation has been used increasingly for malignant disorders, including solid tumors [1, 2]. GVHD is a major complication and a leading cause of morbidity and mortality in recipients of allogeneic stem cell transplantation. GVHD results from immunologic attack by the donor immune cells on the tissues and organs of the recipient. Skin, gastrointestinal tract, and liver are the most commonly targeted organs. The incidence and severity of GVHD can vary depending on the degree of mismatch of major histocompatibility antigens of the donor and host, age of donor and recipient, source of stem cells, and the type of the preparative regimen. With development of non-myeloablative conditioning regimens, the early post-transplant mortality has dropped with more patients developing GVHD. Given the undersupply of related donors, the use of unrelated and partially matched unrelated donors is likely to expand. As our population ages, the use of both older donors and recipients will become more frequent [3]. These factors are likely to increase the incidence of GVHD in the coming years.

Traditionally, GVHD was classified arbitrarily as acute (occurring within 100 days of transplant) and chronic (occurring 100 days or more after transplant) [4]. Overall, up to seventy percent of patients who survive more than 100 days after transplantation will develop the chronic form of GVHD with the majority manifesting in the first year [5-8]. Chronic GVHD has many features of known autoimmune diseases, such as lupus, lichen planus, and scleroderma, and can have a varied clinical presentation. Mononuclear cellular infiltrates can be found in many areas of the graft recipient, including the liver, skin, oral mucosa, and salivary glands.

In order to provide prognostic and treatment guidelines, chronic GVHD has been classified as limited and extensive depending on the number of the organs involved and the severity of the disease [3]. Limited chronic GVHD was defined as isolated skin involvement less than 50% with or without liver dysfunction and did not require systemic immunosuppression. In contrast, extensive chronic GVHD had evidence of skin, mouth, eyes, liver or other target organ involvement. A more recent classification based on several

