## 2.3 GVHD Prophylaxis

07-H-0005

[name].

February 3, 2021

Amendment AA

Currently, all subjects undergoing stem cell transplantation receive some form of acute GVHD prophylaxis with systemic immunosuppressive agents, most commonly cyclosporine with methotrexate. The duration of this regimen is based on past studies where the majority of severe GVHD occurred in the first 100 days post transplant. Therefore, subjects typically are maintained on immunosuppression for the first 100 days which in the absence of clinical GVHD is thereafter tapered. Although widely accepted, this arbitrary time point for initiation of immunosuppression withdrawal may not be ideal for all subjects as some subjects may benefit from earlier withdrawal of immunosuppression to boost the anti-tumor effect of the graft. Conversely, subjects with impending GVHD may benefit from longer duration of prophylaxis.

Attempts to prevent chronic GVHD by systemic immunosuppression have been largely unsuccessful [17, 18]. There are no human studies to our knowledge that have evaluated the possibility of topical or local modalities for chronic GVHD prevention. If proven effective, topical or local therapies could be very useful for chronic GVHD prevention given their general lack of systemic side effects.

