### **4.3 Subject Registration and Prophylactic Treatment Randomization**

Subjects will be recruited from NIH Clinical Center and the surrounding transplant clinics. After confirmation of eligibility and execution of an informed consent, the Principal Investigator or the research nurse will notify the pharmacy of the subject's enrollment and the pharmacy will randomize the subject to therapy. Both investigators and subjects will be blinded to the group assignment until the completion of the study. Assignment of treatment will be done using a block randomization scheme with the assignment probability remaining fixed over the course of the trial. Construction of the randomization schedule is done by pharmacy using a table of random numbers. Subjects will be stratified by the type of conditioning (myeloablative vs. non-myeloablative) to ensure comparable groups.

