### **5.2.2 *Post transplant medications***

There will be no prohibited interventions for this study except topical agents for oral GVHD. All interventions and medications dictated by the subject's primary transplant protocol and clinical necessity will be permitted. Subjects will be queried at interim assessments regarding topical and systemic analgesic use. Factors that can potentially confound the results (such as systemic steroids and other immunosuppressants) will be tracked and taken into consideration at the time of the final statistical analysis.

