### **6.2 On Study Drug Interim Assessments (1 month and 2 month phone contact)**

The NIH research team will contact the subject by clinical appointment, telephone or email at 1 month and 2 months (+/- 2 weeks) after initiation of study drug to inquire about adverse effects and the use of concurrent medications. Laboratory assessments done as part of their post transplant monitoring will also be reviewed when available. Subjects will be asked to return to clinic when clinically indicated and the following questionnaires will be completed at the time of contact.

- Concomitant meds (immunosuppressive, antimicrobial and analgesics)
- The 0-10 Scale for Oral Pain (see Appendix A)
- The 0-10 Scale for Oral Xerostomia (see Appendix A)
- Patient-assessed Global Scale (perception of changes in oral condition)

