### 8.5 Data Analyses

This study will be analyzed according to the “intent to treat” principle, that is, all randomized subjects will be included. Subjects not evaluated for endpoints will be considered to have reached the primary endpoint. Every effort will be made to reach and evaluate the subjects at the monthly intervals and at the end of the 3 month intervention period. The differences in proportions of significant oral chronic GVHD will be assessed by a chi-squared test (with continuity correction). Treatment group differences in the severity scores, pain and xerostomia scores, and quality of life scores (OHIP-14) will be assessed using the Wilcoxon test. Adjustments will be made for age and other covariates of interest, such as systemic immunosuppression. Adverse events will be tabulated by severity and treatment assignment. For pediatric subjects, analyses will include growth assessment (growth chart [length for age, weight for age percentiles

and body mass index] for age percentiles) and bone age and the associated z-scores (the number of standard deviations the child's measures [weight, height etc] differ from the population mean).

The intervention period will be 3 months. Should the subject reach the primary endpoint (development of clinically significant oral chronic GVHD), the subject will be asked to participate in end of study assessments and then will go off study. Subjects who did not develop oral chronic GVHD in the intervention phase of the study will be followed for up to 6 months to document late development of oral chronic GVHD. All subjects will be evaluated after 6 months after completion of the intervention phase of the study in the absence of clinical oral GVHD. Final statistical analysis will be performed once all subjects in the sample have completed the study and all records have been collected. We will use stratified analyses to account for effects of systemic immunosuppressive agents and other prognostic factors.

In the event of a protocol violation, the aggregate data will be analyzed with and without those subjects involved in the incident.

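### Section 8.5 tests the primary endpoint without the conditioning stratum used at randomisation, and leaves the timing, model and endpoint of the immunosuppression adjustment open

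*Combined protocol and SAP*

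**What the plan says.** Randomisation (section 4.3) is in blocks, with this stratification: "Subjects will be stratified by the type of conditioning (myeloablative vs. non-myeloablative) to ensure comparable groups". Section 2.1 gives the factors with which GVHD incidence and severity vary, among them "age of donor and recipient, source of stem cells, and the type of the preparative regimen".

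For the primary endpoint, section 8.5 names one test: "The differences in proportions of significant oral chronic GVHD will be assessed by a chi-squared test (with continuity correction"). No stratum is attached to it, and conditioning type is not named anywhere in 8.5.

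Section 8.5 then makes two further commitments: "Adjustments will be made for age and other covariates of interest, such as systemic immunosuppression", and, later, "We will use stratified analyses to account for effects of systemic immunosuppressive agents and other prognostic factors". Section 5.2.2 says of possible confounders: "such as systemic steroids and other immunosuppressants) will be tracked and taken into consideration at the time of the final statistical analysis". The contacts at months 1 and 2 (section 6.2) collect "Concomitant meds (immunosuppressive, antimicrobial and analgesics"), and the same item recurs at month 3 (section 6.3). No section says which of these values enters an efficacy analysis, in what model, or for which endpoint.

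**The concern.** The first issue is a mismatch between design and analysis. Blocking within conditioning strata balances the arms on that factor. If the factor predicts the outcome, a test that ignores it overstates the variance of the difference, so the true type I error drifts below nominal and some power is lost. What is at stake is efficiency, not validity.

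The second issue is that systemic immunosuppression after randomisation is not a pure baseline characteristic. Section 2.3 describes a taper after day 100 that depends on the absence of clinical GVHD, and section 2.4.1 says GVHD is treated with systemic immunosuppressive agents. An efficacy analysis adjusted for, or stratified by, on-study use could therefore condition on a consequence of GVHD. With timing, model and endpoint all open, the adjusted result that is reported could also be chosen after the data are seen.

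**Working it through.** **Inputs.** From section 8.2: 36 per arm, 15% versus 45%, significance level 0.05 (taken as two-sided; the plan does not say). From 8.5: continuity-corrected chi-squared. From 4.3: two conditioning strata. Assumed, because the documents give neither risk by conditioning type nor the stratum mix: stratum odds ratio (OR) from 1 to 8, several stratum splits, and equal arms within each stratum.

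**The plan's own figure.** Without continuity correction, n per arm = [1.96·√(2·0.30·0.70) + 0.8416·√(0.15·0.85 + 0.45·0.55)]² / 0.30² = (1.270 + 0.515)² / 0.09 = 35.4, so 36, with power 80.7% at 36. The stated 36 per arm reproduces. The power figures below start near 74% because they use the corrected test that 8.5 names; that gap is a separate matter and is not counted here.

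**Tests compared.** With n = 36 per arm, N = 72, m total events, and a, b the events in the two arms:

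- Planned: N·(|a(n−b) − b(n−a)| − N/2)² / [n²·m·(N−m)].
- CMH, summing over strata with h per arm, N_s = 2h and m_s events: (|Σ(a_s − h·m_s/N_s)| − 0.5)² / Σ[h²·m_s·(N_s−m_s) / (N_s²·(N_s−1))].

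Both are compared with 3.84. For each OR, the stratum risks were solved so that the arm totals stay at 15% and 45% (power) or 30% and 30% (size). Probabilities were summed exactly over all possible tables; simulations of 200,000 trials agree to about 0.2 point.

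**Equal strata (18/18 per arm), all entries in %; stratum risks are lower/higher stratum**

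| OR | Risks, 15% arm | Risks, 45% arm | Power, planned | Power, CMH | Change (points) | Size, planned | Size, CMH |
|---|---|---|---|---|---|---|---|
| 1 | 15.0/15.0 | 45.0/45.0 | 74.17 | 73.63 | -0.54 | 2.77 | 2.67 |
| 2 | 10.7/19.3 | 36.5/53.5 | 74.40 | 74.56 | +0.16 | 2.59 | 2.65 |
| 4 | 7.0/23.0 | 28.5/61.5 | 75.05 | 76.65 | +1.60 | 2.11 | 2.46 |
| 6 | 5.2/24.8 | 24.2/65.8 | 75.60 | 78.42 | +2.82 | 1.78 | 2.35 |
| 8 | 4.2/25.8 | 21.4/68.6 | 76.04 | 79.98 | +3.94 | 1.55 | 2.31 |

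The 2.77% at OR 1 reflects the continuity correction alone. The further fall to 1.55% is what ignoring the stratum adds.

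**Unequal strata (lower-risk stratum first), corrected power, planned to CMH**

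- 27/9 per arm: OR 1, 74.17 to 73.53 (-0.64); OR 8, 75.81 to 80.62 (+4.81).
- 9/27 per arm: OR 1, 74.17 to 73.53 (-0.64); OR 8, 75.18 to 76.29 (+1.11).
- 33/3 per arm: OR 1, 74.17 to 73.00 (-1.17); OR 2, 74.25 to 73.23 (-1.02); OR 4, 74.50 to 74.29 (-0.21).

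**Immunosuppression.** Here the passages have to be read side by side. Sections 5.2.2, 6.2 and 6.3 record use after randomisation. Sections 2.3 and 2.4.1 make that use depend partly on GVHD. Section 8.5 adjusts for it with no time point. Against this, sections 5.3 and 8.8.2 take subjects off study once they reach the primary endpoint, so treatment given because of the endpoint is largely absent from the data. What remains is a path through oral GVHD below score 3 and GVHD at other sites. The documents give no rate for either, nor for on-study immunosuppressant use, so no size can be calculated.

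**The case against.** The strongest reply on the stratum is that this is a preference. The planned test controls type I error, the gain is 1.6 points or less up to an odds ratio of 4 with equal strata, and nothing in the documents supports any particular odds ratio. If one stratum is very small, CMH loses a little even at an odds ratio of 2. The promise to stratify for other prognostic factors could also be read to include conditioning, given sections 2.1 and 4.3. Most of this stands. But 8.5 neither names conditioning nor ties that promise to the primary test, and following the randomisation costs almost nothing.

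On immunosuppression, the reply is that a baseline reading of 8.5 is open, that the off-study rule cuts the main path, and that this is a pilot trial. That also stands, and it limits the point to under-specification with a possible distortion.

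A reader might infer more than the documents support:

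- *That the primary test is invalid or anticonservative.* The size column shows the opposite.
- *That the adjustment is assigned to supporting and secondary analyses.* Section 8.5 names no endpoint. The inference is reasonable, since neither the chi-squared nor the Wilcoxon test takes covariates, but it remains an inference.
- *That the adjustment will materially shrink the estimated effect.* If use were assumed at 60% or 80% after GVHD and 30% without it, a true -30-point difference would shrink to -27.9 or -24.2. That models treatment following the endpoint, which sections 5.3 and 8.8.2 largely remove, so it does not estimate what would happen here.
- *That the cost of the continuity correction belongs to this point.* Section 8.5 already says the correction is used; its fit with section 8.2 is a separate question.

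**Conclusion.** The point holds as a recommended improvement, with medium confidence; it is not a validity fault. Leaving conditioning out makes a valid test more conservative if conditioning is prognostic. Including it is worth between a loss of about 0.5 to 1.2 points of power (conditioning not prognostic, the loss largest when one stratum is very small) and a gain of about 4 points (odds ratio 8, equal strata; 4.8 with a 27/9 split). All of this rests on assumed odds ratios and stratum mixes, two-sided 5% testing, and the 15% and 45% of section 8.2.

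The immunosuppression part is secondary and conditional. The missing time point, model and endpoint are plain from the text. Whether any distortion follows depends on which values are used; its size is unknown and may be small, and the named primary test is not affected.

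**What to change.** In section 8.5:

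1. Make the primary test Cochran-Mantel-Haenszel stratified by conditioning type, with the same continuity-correction choice as the plan. This is a wording change; its price is the possible power loss given above.
2. Limit covariates and strata in any adjusted efficacy analysis to values fixed before the first dose: conditioning type, age, and immunosuppressive agent or intensity (for example agent class or number of agents). Name the model and the endpoints. A yes/no value would be nearly constant, since section 2.3 says "all subjects undergoing stem cell transplantation receive some form of acute GVHD prophylaxis with systemic immunosuppressive agents" and that they typically stay on it for the first 100 days. This applies to efficacy only; the adrenal analysis in 8.4.6 is a different question.
3. Report on-study immunosuppression by arm descriptively, or as a labelled exploratory analysis. This needs wording only.

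Item 2 carries a data cost. The screening medication review at days 60-90 is done under the parent transplant or screening protocol (6.1.1), and the baseline list in 6.1.2 has no medication item. Agent or intensity must be abstracted from the parent record, where it can be, and may be out of date by the first dose. A medication item could be added at the day 90-100 reassessment (8.8.2), but only for subjects who have not yet passed it. The documents do not state accrual status, so for those already past it abstraction is the workable route.

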## **8.6 Interim Analysis**

There will be no interim analysis due to the short and preliminary nature of this study.

## **8.7 Stopping Rule**

There will be no interim statistical analysis given the small preliminary nature of the study. We do not expect dramatic efficacy or significant difference in serious adverse effects that would require stopping the trial early. The study medication is a safe and non-toxic agent commonly used for the prophylaxis of oral chronic GVHD and other oral mucosal conditions. All the procedures specifically related to this protocol are standard diagnostic procedures and are associated with few complications. In the event of a serious adverse event related to the study medication or procedure the IRB will be notified immediately.

## **8.8 Off Study Criteria**

### **8.8.1 Subject choice:**

Subjects may withdraw from the study at their request any time. The risks of withdrawing will be discussed, as will alternative treatment options. Those subjects who choose to withdraw will be strongly encouraged to participate in post therapy assessments until he/she initiates alternative chronic GVHD therapy or through the 6 month off study medication mark to assess for late occurring adverse events.

### **8.8.2 Principal investigator decision:**

Subjects will be taken off study during the 3 month study drug administration period:

- if they develop oral chronic GVHD in the period between baseline assessments and first dose of study drug (subjects will be reassessed between post-transplant days 90 and 100 to ensure absence of oral chronic GVHD and reinforce protocol procedures)
- if they are unable to comply with the study visits or become severely ill and cannot comply with the intervention
- if they reach the primary endpoint of clinically significant oral chronic GVHD
- if they have relapse of their underlying disease (leukemia subjects, see section 10.3.1 risk of tumor lysis)

These subjects will be asked to complete the required off study drug evaluations and end of study assessments.

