### **8.3 Primary Endpoint**

The primary objective of this study is to evaluate the safety and efficacy of topical dexamethasone 0.01% solution used as an oral rinse for prevention of oral chronic graft versus host disease. The primary endpoint is the proportion of subjects that develop clinically significant (severity score 3 or higher) oral chronic GVHD by three months post dexamethasone administration. For the purposes of this study, oral chronic GVHD with the objective score of 3 or higher on a 6-point oral GVHD scale (Appendix C) will be considered clinically significant. An intention to treat analysis will be conducted as the primary analysis.

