- Acute tumor lysis: Two cases of acute tumor lysis syndrome in patients with acute leukemia have been reported in the literature following dexamethasone for prophylaxis of peri-operative nausea and vomiting; one of which was fatal (patient had a new onset of undiagnosed acute leukemia). Although the dexamethasone on this study is administered as an oral rinse (not swallowed), low levels (exact rate unknown) of topical steroids are absorbed through the oral mucosa. Although it is very unlikely that acute tumor lysis would occur in our study, in the event of disease relapse in leukemia subjects, the study drug will be stopped, and the subject will go off-study (see section 8.8.2)

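### Relapse and inability to use the rinse take a subject off study, not just off drug, so three-month GVHD status goes unobserved in an intention-to-treat endpoint

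*Combined protocol and SAP*

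**What the plan says.** Section 8.8.2 lists the reasons for which the investigator takes a subject off study during the drug period. Two matter here. One covers subjects who "become severely ill and cannot comply with the intervention". The other applies "if they have relapse of their underlying disease (leukemia subjects, see section 10.3.1 risk of tumor lysis". Section 10.3.1 confirms both steps for leukemia: "in the event of disease relapse in leukemia subjects, the study drug will be stopped, and the subject will go off-study".

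On what follows, section 8.8.2 says: "These subjects will be asked to complete the required off study drug evaluations and end of study assessments". Section 6.5 places the end-of-study visit at premature withdrawal, and its list includes the Appendix C scale. The off-drug evaluations are neither defined nor dated. The month-3 Appendix C examination is in section 6.3, at three months plus or minus 7 days from the start of study drug.

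Section 8.3 defines the primary endpoint as an Appendix C score of 3 or higher "by three months post dexamethasone administration", with intention to treat as the primary analysis. Section 8.5 includes everyone randomised, sets the rule "Subjects not evaluated for endpoints will be considered to have reached the primary endpoint", and undertakes to make every effort to "reach and evaluate the subjects at the monthly intervals and at the end of the 3 month intervention period". For voluntary withdrawals only, section 8.8.1 adds: "Those subjects who choose to withdraw will be strongly encouraged to participate in post therapy assessments".

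**The concern.** Outcome collection is tied to treatment. A subject who can no longer use the rinse, or who relapses, can often still have the mouth examined at month 3. The tumor-lysis reasoning in section 10.3.1 explains stopping the drug; it gives no reason to stop the examination. Because the analysis keeps every randomised subject, status that is not observed has to be assumed.

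Section 8.5 also leaves open which assumption applies. Take a subject who relapses in week 5 with an exit score of 1. The subject was examined, so could be a non-event. The subject was not examined for three-month status, so could fall under the not-evaluated rule and be an event. Two analysts could score the same subject in opposite ways.

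At stake are misclassification of the primary endpoint, bias if such exits differ between arms, and a scoring choice that might be made after the data are seen.

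**Working it through.** **1. Does any provision require a month-3 examination after an early exit?**
- Sections 8.8.2 with 6.5: an Appendix C examination at exit. A score of 3 or higher there is an event. A score below 3 does not show status at month 3.
- Section 8.8.2, off-drug evaluations: undated. Section 6.3 is a possible referent, but it is timed from drug start and nothing tells off-study subjects to return then.
- Section 8.5, every effort: a general intent, which does not override the specific off-study rule.
- Section 8.8.1: encourages later assessments, but only for subjects who choose to withdraw.

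None of them requires it.

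**2. The plan's own figure.** Section 8.2 gives 36 per arm, 15% v 45%, significance level 0.05 and 80% power. The usual normal approximation, two-sided and uncorrected, is

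power = Φ[(|p1 − p2|√n − 1.96√(2p̄(1 − p̄))) / √(p1(1 − p1) + p2(1 − p2))]

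With p̄ = 0.30 this is Φ[(0.3 × 6 − 1.96 × 0.648) / 0.612] = Φ(0.865) = 0.807, so the 80% reproduces. Section 8.5 names the continuity-corrected test. Exact enumeration of two binomials, rejecting when the corrected p is below 0.05, gives 0.742 at 36 per arm and 0.804 at 41 per arm (82/2, the accrual cap). The gap between 0.807 and 0.742 comes mainly from the continuity correction and is separate from this point.

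**3. What the open scoring rule does.** Let d be the share of subjects who exit early with a score below 3, equal in both arms. The documents do not give d. The range used is 2–3% (about 1 or 2 of 72 subjects, an assumption) up to 10% (section 8.2's ceiling for all drop-outs, so an upper bound for these reasons). Exits are taken to precede any event.
- Counted as events, the rate is d + (1 − d)p. At d = 10%: 0.10 + 0.90 × 0.15 = 0.235, and 0.10 + 0.90 × 0.45 = 0.505.
- Counted as non-events, the rate is (1 − d)p. At d = 10%: 0.135 and 0.405.

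| n per arm | d | power, exits as events | power, exits as non-events | trials where the two disagree at p < 0.05 |
|---|---|---|---|---|
| 36 | 0 | 0.742 | 0.742 | 0 |
| 36 | 2% | 0.708 | 0.727 | 8% |
| 36 | 3% | 0.692 | 0.720 | 11% |
| 36 | 10% | 0.573 | 0.666 | 22% |
| 41 | 0 | 0.804 | 0.804 | 0 |
| 41 | 2% | 0.773 | 0.791 | 7% |
| 41 | 3% | 0.757 | 0.785 | 10% |
| 41 | 10% | 0.655 | 0.734 | 20% |

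The last column comes from the joint distribution of observed events and exits in each arm. The non-event powers are floors: if the exit examination catches half of these subjects' events, d = 10% gives 0.705 (36 per arm) and 0.771 (41 per arm).

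**4. One subject near the boundary.** Corrected chi-squared, 36 per arm:
- 5 v 14 events: 72(|5 × 22 − 14 × 31| − 36)² / (36 × 36 × 19 × 53) = 4.58, p = 0.032.
- One dexamethasone exit recoded as an event, 6 v 14: 72(|6 × 22 − 14 × 30| − 36)² / (36 × 36 × 20 × 52) = 3.39, p = 0.066.

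**5. Would the retained visit add power?** If it recovers half of a 10% exit rate and the rest count as events, d is effectively 5% and power at 36 per arm is 0.658. Accepting exit scores as non-events gives 0.666. So it would not.

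**6. False-positive rate.** With 25% in both arms, 36 per arm and equal exits, rejection is 0.0267 with no exits, and 0.0279 (events) or 0.0263 (non-events) at 10%.

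**The case against.** The plan does not abandon these subjects. An exit examination is requested, an exit score of 3 or higher already counts, and the not-evaluated rule, read with the three-month endpoint, plausibly covers a subject last scored below 3 at week 5. One sentence in section 8.5 would settle the scoring and remove every disagreement figure above without touching section 8.8.2. The 5 v 14 table is a chosen borderline case. The exit rate is assumed, and section 4.2.4 excludes life expectancy under four months, which screens out some of the sickest. Sparing a relapsed patient a trip to the NIH in a pilot study is a defensible choice. A score after relapse may reflect changed immunosuppression as much as the rinse.

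Much of this stands. The figures measure the scoring ambiguity, not the value of the visit, and the bias that the visit would prevent is not quantified. What does not fall is the structural point: a scoring sentence alone makes the assumption uniform but leaves status assumed. Replacement under section 8.2 does not answer it either, because that section does not say how a replaced subject counts and section 8.5 keeps everyone randomised. Immunosuppression is already tracked and adjusted for (sections 5.2.2 and 8.5).

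A reader might infer that these subjects are never examined; sections 8.8.2 and 6.5 say otherwise. A reader might also take the 7–22% as an error rate of the trial; it only compares two extreme codings of every exit under assumed rates.

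**Conclusion.** The concern holds as a design weakness with a cheap remedy. Sections 8.8.2 and 10.3.1 end participation where stopping the drug would do, and no provision then requires the examination that the three-month intention-to-treat endpoint needs. Section 8.5 does not say how an earlier score below 3 counts.

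The gain from a change is observed status in place of assumed status: less misclassification, and less bias if exits differ by arm. Its size is unknown, because the documents give no rate for relapse or illness exits and no split by arm. The 2–10% range and equal exits in both arms are assumptions.

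Two stronger conclusions are tempting and unsupported. One is that keeping the visit restores power: at a 10% exit rate with half recovered, it does no better than the non-event scoring. The other is that the false-positive rate is inflated: with equal exits it hardly moves, and the documents give nothing from which to work out an unequal case.

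**What to change.** - **Sections 8.8.2 and 10.3.1:** make relapse and inability to use the rinse reasons to stop study drug only. Keep the section 6.3 month-3 Appendix C examination for every randomised subject who is alive, still consenting, able to attend and not already scored 3 or higher.
- **Section 8.5:** state that an exit score below 3 before month 3 does not replace that examination, and that the existing not-evaluated rule applies if it is not done. Add a sensitivity analysis counting such subjects as non-events. This sentence also covers subjects removed because they cannot keep study visits, for whom the same scoring question arises.

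The cost is a few sentences of amendment and one already-scheduled NIH visit for a few ill subjects. Some will be unable to travel and will still be missing, and under the not-evaluated rule they would count as events, which is why the sensitivity analysis is needed. Scores after relapse should be read alongside the recorded immunosuppression. The wording should be settled before unblinding.
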